- u. Proportion of patients reaching normal B-hb levels (men: 134–167 g/L, women: 117–155 g/L) and change from baseline in B-hb levels at week 8/16/24/52.
- v. Proportion of patients reaching normal B-leuk levels (3.4-8.2 x 10^9 /L) and change from baseline in B-leuk levels at week 8/16/24/52.

- w. Proportion of patients reaching normal B-Thromb (150–360 x 10^9 /L) and change from baseline in B-Thromb levels at week 8/16/24/52.
- x. Proportion of patients reaching normal B-ly (1.3-3.6x 10⁹/L) and change from baseline in B-ly levels at week 8/16/24/52.
- y. Proportion of patients reaching normal B-neutr (1.5-6.7 x $10^9/L$) and change from baseline in B-neutr levels at week 8/16/24/52.
- z. Proportion of patients reaching normal P-alb (18-39 years: 36-48 g/L, 40-69 years: 36-45 g/L, 70 years and over: 34-45 g/L) and change from baseline in P-alb levels at week 8/16/24/52.
- aa. Proportion of patients with extended to facitinib induction dose (additional 8 weeks with 10mg).
- bb. Real-world dosing of tofacitinib, e.g., usage of a higher dose (10 mg) as maintenance therapy.
- cc. Survival without drug discontinuation, colectomy or UC-related hospitalization (using time to event analysis).

Secondary objective 2 - To Assess Treatment Lines Prior to Tofacitinib Treatment.

a. Number and type of previous UC treatments.

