4.4 SUBGROUPS

5 ENDPOINTS AND COVARIATES

5.1 EFFICACY/EFFECTIVENESS ENDPOINT(S)

- Proportion of patients who are taking to facitinib at week 8, 16, 24 and 52
- Rate of clinical remission
- Rate of clinical response
- Proportion of patients in steroid-free clinical remission
- Proportion of patients reaching clinical response
- Time to response
- Proportion of responders defined by a f-calpro reduction of $\geq 50\%$, $\geq 75\%$ or $\geq 90\%$
- Proportion of patients reaching f-calpro below 250 mg/kg of those that had f-calprotectin above 250 mg/kg at baseline
 - o change from baseline in f-calpro
- Proportion of patients in sustained remission (pMayo and full Mayo score) from week 8 to week 16, 24 and 52
- Proportion of patients in sustained remission (pMayo and full Mayo score) from week 16 to week 24 and 52
- Proportion of patients in sustained steroid free remission (pMayo and full Mayo score) at week 16 to 24 and 52 (for all patients and for those treated with corticosteroids at baseline).
- Change in partial and full Mayo score
- Proportion of patients in sustained endoscopic remission (sub score = 0), mucosal healing (sub score 0-1) or endoscopic response (sub score reduction from baseline of ≥1) from week 8 to week 16, 24 and 52
- Proportion of patients in physician assessed histological remission determined as inactive disease
 - o change from baseline in histology assessment

- Proportion of patients in sustained steroid free remission (pMayo and full Mayo score) (for all patients and for those treated with corticosteroids at baseline) and endoscopic remission (sub score = 0), mucosal healing (sub score 0-1) or endoscopic response (sub score reduction from baseline of ≥1) from week 8 to week 16, 24 and 52
- Proportion of patients with corticosteroid tapering
 - o tapering rates and doses
- Proportion of patients with improvement in stool frequency sub score of 1 or more points
 - o change from baseline in stool frequency sub score
- Proportion of patients with improvement in rectal bleeding sub score of 1 or more points
 - o change from baseline in rectal bleeding sub score
- Proportion of patients reaching normal P-CRP/B-hb/B-leuk/B-Thromb/B-ly/B-neutr/P-alb levels
 - o and change from baseline levels
- Proportion of patients reaching normal B-hb levels
 - o change from baseline in B-hb levels
- Proportion of patients with extended to facitinib induction dose (additional 8 weeks with 10mg).
- Real-world dosing of to facitinib

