7.2 STATISTICAL ANALYSES

Primary objectives a-e:

Describe the patient population at the baseline (initiation of tofacitinib), using the data collected. For each continuous variables (age, BMI, age at diagnosis, duration of disease, laboratory measures), provide the mean, median, sd, 25%Q and 75%Q values. For categorical variables (sex, smoking status, extent of colonic involvement, disease severity, endoscopic findings), report the number of patients, and proportion. Report proportion of missing values if present.

Secondary objective - Assess the Real-world Effectiveness of Tofacitinib

Secondary objective a:

For each patient, define the "on treatment" as Yes/No based on the latest available dose (at each timepoint 8, 16, 24 and 52 weeks). Patients marked with "not on treatment" prior to timepoint will be regarded as discontinued.

Report the proportion of patients on treatment, not censored at each timepoint.

Secondary objectives b, c, d, e, g, n:

For each patient, define the fulfilment of the remission/response criteria as Yes/No based on the latest available data (at each timepoint 8, 16, 24 and 52 weeks).

Report the proportion of patients on fulfilling the response/remission criteria, not censored at each timepoint.

Secondary objective f:

Define the time of response for each patient as first ever data-entry that fulfils response criteria. Fit competing-risk time-to-event model to the data, with time-to-event defined as time from index until response (event) or discontinuation (competing event), or end of data collection (censoring event).

Assess the cumulative incidence as function of time for both types of events. Illustrate the Aalen-Johansen state probabilities of multistate model.

Secondary objective h:

Select only patients with baseline f-calprotectin above 250 mg/kg at baseline. For each subsequent f-calprotectin measure, define below 250 mg/kg as Yes/No variable. Additionally, estimate the absolute delta change per baseline value.

For each timepoint (week 8, 16, 24 and 52), report the proportion of patients on fulfilling the <250mg/kg criteria, and summary statistics (mean, median, sd, 25%Q and 75%Q) of delta change, among patients not censored at each timepoint.

Secondary objectives i, j, k, m, o:

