Select only patients that were on remission/steroid free remission at the timepoints. For each patient, define the fulfilment of the remission/response criteria as Yes/No based on the latest available data (at each timepoint 16, 24 and 52 weeks). Report the proportion of patients on fulfilling the remission criteria, not censored at each timepoint.

Secondary objective l:

For each available Mayo score (full or partial), estimate the absolute delta change from baseline value. For each timepoint (week 8, 16, 24 and 52), report the summary statistics (mean, median, sd, 25%Q and 75%Q) of delta change, among patients not censored at each timepoint.

Secondary objective p:

Perform analyses described in secondary objective b and c, stratified by the extent of colonic involvement

Secondary objective q:

For each patient, define the corticosteroid tapering as Yes/No based on the latest available data (at each timepoint 8, 16, 24 and 52 weeks). Additionally, define the tapering rates and doses based on latest available data.

For each timepoint (week 8, 16, 24 and 52), report the proportion of patients that had corticosteroid tapered, among patients not censored at each timepoint. Additionally,

report summary statistics (mean, median, sd, 25%Q and 75%Q) of tapering rates and doses among patients that had corticosteroids tapered.

Secondary objectives r and s:

For each patient, define the fulfilment of the improvement criteria as Yes/No based on the latest available data (at each timepoint 8, 16, 24 and 52 weeks). Additionally, estimate the absolute delta change per baseline value

Report the proportion of patients on fulfilling the response/remission criteria, report the summary statistics (mean, median, sd, 25%Q and 75%Q) of delta change, among patients not censored at each timepoint.

Secondary objectives t-z:

For each subsequent laboratory measure, define "normal-level" as Yes/No variable. Additionally, estimate the absolute delta change per baseline value. For each timepoint (week 8, 16, 24 and 52), report the proportion of patients on fulfilling the "normal-level" criteria and summary statistics (mean, median, sd, 25%Q and 75%Q) of delta change, among patients not censored at each timepoint.

Secondary objective aa:

Report the proportion of patients that received extended induction

Secondary objective bb:

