8 TABLE SHELLS

Table 2: Table shell for patient characteristics for primary objective

				n	missing
Variable	categories	mean (sd)	Median (25Q-75Q)	(%)	%
age				-	
sex	male	-	-		
	female	-	-		
weight				-	
height				-	
(BMI)				-	
smoking	current	-	-		
	ex-smoker	-	-		
	non-smoker	-	-		
age at UC diagnosis				-	
duration of UC				-	
Montreal classification	E1	-	-		
	E2	-	-		
	E3	-	-		
Mayo-score				-	
F-calpro				-	
P-CRP				-	
B-thromb				-	
P-alb				-	
B-leuk				-	
B-ly				-	
B-neutr				-	
B-hb				-	
Endoscopic findings	yes	-	-		
	no	-	-		

Table 3: Table shell for outcome objectives

Objective	Outcome	Week 8	Week 16	week 24	week 52
1	N patients	N	N	N	N
P1 - a	Proportion of patients on treatment	n (%)	n (%)	n (%)	n (%)
P1 - b	Proportion of patients with clinical remission (full Mayo)	n (%)	n (%)	n (%)	n (%)
P1 - b	Proportion of patients with clinical remission (partial Mayo)	n (%)	n (%)	n (%)	n (%)
P1 - c	Proportion of patients with clinical response (partial Mayo)	n (%)	n (%)	n (%)	n (%)
P1 - c	Proportion of patients with clinical response (full Mayo)	n (%)	n (%)	n (%)	n (%)
P1 - d	Proportion of patients with steroid free clinical remission	n (%)	n (%)	n (%)	n (%)
P1 - g	Proportion of patients with f-calpro reduction ≥50%	n (%)	n (%)	n (%)	n (%)
P1 - g	Proportion of patients with f-calpro reduction ≥75%	n (%)	n (%)	n (%)	n (%)
P1 - g	Proportion of patients with f-calpro reduction ≥90%	n (%)	n (%)	n (%)	n (%)
P1 - h	Proportion of patients reaching f-calpro below 250 mg/kg, of those that had f-calprotectin above 250 mg/kg at baseline	n (%)	n (%)	n (%)	n (%)
P1 - h	Change in f-calpro, among patients with f-calprotectin above 250 mg/kg at baseline	Δ -from baseline (mean ± sd)	Δ-from baseline (mean ± sd)	Δ-from baseline (mean ± sd)	Δ-from baseline (mean ± sd)

Objective	Outcome	Week 8	Week 16	week 24	week 52
P1 - i	Proportion of patients in sustained remission (pMayo) from week 8	-	n (%)	n (%)	n (%)
P1 - i	Proportion of patients in sustained remission (full Mayo score) from week 8	-	n (%)	n (%)	n (%)
P1 - j	Proportion of patients in sustained remission (pMayo) from week 16	-	-	n (%)	n (%)
P1 - j	Proportion of patients in sustained remission (full Mayo score) from week 16	-	-	n (%)	n (%)
P1 - k	Proportion of patients in sustained steroid free remission (pMayo) from week 16	-	-	n (%)	n (%)
P1 - k	Proportion of patients in sustained steroid free remission (full Mayo score) from week 16	-	-	n (%)	n (%)

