P1 - u	change from baseline in B-hb levels	(mean ± sd)	(mean ± sd)	(mean ± sd)	(mean ± sd)
	Proportion of patients reaching normal B-leuk				
P1 - v	levels (3.4-8.2 x 10 ⁹ /L)	n (%)	n (%)	n (%)	n (%)
		Δ-from baseline	Δ-from baseline	Δ-from baseline	Δ-from baseline
P1 - v	change from baseline in B-leuk levels	(mean ± sd)	(mean ± sd)	(mean ± sd)	(mean ± sd)
	Proportion of patients reaching normal B-Thromb				
P1 - w	(150–360 x 109/L)	n (%)	n (%)	n (%)	n (%)
		Δ-from baseline	Δ-from baseline	Δ-from baseline	Δ-from baseline
P1 - w	change from baseline in B-Thromb levels	(mean ± sd)	(mean ± sd)	(mean ± sd)	(mean ± sd)

Objective	Outcome	Week 8	Week 16	week 24	week 52
P1 - x	Proportion of patients reaching normal B-ly (1.3-3.6 x 109/L)	n (%)	n (%)	n (%)	n (%)
P1 - x	change from baseline in B-ly levels	Δ-from baseline (mean ± sd)	Δ-from baseline (mean ± sd)	Δ -from baseline (mean ± sd)	Δ-from baseline (mean ± sd)
P1 - y	Proportion of patients reaching normal B-neutr (1.5-6.7 x 109/L)	n (%)	n (%)	n (%)	n (%)
P1 - y	change from baseline in B-neutr levels	Δ -from baseline (mean ± sd)	Δ -from baseline (mean ± sd)	Δ-from baseline (mean ± sd)	Δ-from baseline (mean ± sd)
P1 - z	Proportion of patients reaching normal P-alb (18-39 years: 36-48 g/L, 40-69 years: 36-45 g/L, 70 years and over: 34-45 g/L)	n (%)	n (%)	n (%)	n (%)
P1 - z	change from baseline in P-alb levels	Δ -from baseline (mean ± sd)			
P1 - bb	Proportion of patients with higher dose (10mg) of tofacitinib	n (%)	n (%)	n (%)	n (%)

Table 4: table shell to repost previous treatments

	Value
	mean ±
Number of treatments	sd
corticosteroids	n (%)
5-ASA	n (%)
Azathioprine	n (%)
6-Merkatopurin	n (%)
Methotrexate	n (%)
Cyclosporine	n (%)
Ustekinumab	n (%)
Vedolizumab	n (%)
Adalimumab	n (%)
Infliximab	n (%)
Golimumab	n (%)

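### SAP 7.2, objectives t–z: rows headed as *reaching* normal include patients already normal at baseline, and no planned output gives the share normal at baseline

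*SAP*

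**What the plan says.** Objectives t–z cover P-CRP, B-hb, B-leuk, B-thromb, B-ly, B-neutr and P-alb. The analysis text in SAP 7.2 reads "For each subsequent laboratory measure, define 'normal-level' as Yes/No variable". It then reports the proportion meeting that definition at the four timepoints, over patients still uncensored, together with change-from-baseline summaries. Nothing is conditioned on the baseline value.

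The names given to this output suggest a change of state. SAP 5.1 lists "Proportion of patients reaching normal P-CRP/B-hb/B-leuk/B-Thromb/B-ly/B-neutr/P-alb levels" and repeats B-hb on a line of its own. Seven Table 3 headings use the same verb; the neutrophil row begins "Proportion of patients reaching normal B-neutr (1.5-6.7 x 109/L". The objectives in SAP 2.2 and protocol section 7.3.1 are worded the same way, for example "Proportion of patients reaching normal B-hb levels (men: 134–167 g/L, women: 117–155 g/L".

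Objective h is handled differently. Its analysis begins "Select only patients with baseline f-calprotectin above 250 mg/kg at baseline", and its Table 3 heading carries the restriction: "Proportion of patients reaching f-calpro below 250 mg/kg, of those that had f-calprotectin above 250 mg/kg at baseline".

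For baseline, SAP 7.2 says "For each continuous variables (age, BMI, age at diagnosis, duration of disease, laboratory measures), provide the mean, median, sd, 25%Q and 75%Q values". The variables to be counted are given separately: "For categorical variables (sex, smoking status, extent of colonic involvement, disease severity, endoscopic findings), report the number of patients, and proportion". No laboratory marker is among them. Table 2 has a dash in the n (%) cell of every laboratory row, and the Table 3 columns start at week 8.

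**The concern.** These rows fall under the real-world effectiveness objective, where a reader will take *reaching normal* to mean moving from abnormal to normal. What is calculated is the share normal at a timepoint, which mixes patients who normalised with patients who were never abnormal. Row h and rows t–z would stand in one table, with the same verb, and measure different things.

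The visible entry criteria do not require any of the seven markers to be abnormal. The SAP's definition of active disease is not among those criteria, and it rests on endoscopy or calprotectin, so it would not ensure this either.

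Without the baseline share, the rows can be read neither as normalisation nor as a change in the proportion normal. Protocol section 8.6 allows only aggregate results to leave the analysis environment, so an outside reader could not recover the figure later.

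**Working it through.** The documents state no rate on this point, so there is no figure of the plan's own to reproduce. The only documented number used is the expected N of 100–150 (SAP 2.1). Everything else is assumed and shown over a range.

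**1. What the row measures.** Let q be the share normal at baseline, k the share of those still normal at the timepoint, and r the share of baseline-abnormal patients who have become normal. Then

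row = q·k + (1 − q)·r.

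**2. Limiting case.** With k = 1 and r = 0, row = q. An assumed q of 30, 50 or 70% gives a row of 30, 50 or 70% although nobody normalised.

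**3. Reading a result backwards.** Rearranged, r = (row − q·k)/(1 − q). For an illustrative row of 65%:

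| q | r if k = 1 | r if k = 0.9 |
|---|---|---|
| 0.2 | (0.65 − 0.20)/0.8 = 56% | (0.65 − 0.18)/0.8 = 59% |
| 0.4 | (0.65 − 0.40)/0.6 = 42% | (0.65 − 0.36)/0.6 = 48% |
| 0.6 | (0.65 − 0.60)/0.4 = 12.5% | (0.65 − 0.54)/0.4 = 27.5% |

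One reported figure is compatible with normalisation anywhere from 12.5% to 59%, depending mostly on q.

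**4. Can q be recovered from the planned tables?**
- P-CRP has a single limit (below 4 mg/L), so quartiles bracket q. A lower quartile above 4 means no more than about 25% were normal; a median below 4 means at least half were.
- B-leuk, B-thromb, B-ly and B-neutr have two-sided ranges, so quartiles say less. If both quartiles lie inside the range, at least half were normal, but not how many more.
- B-hb limits depend on sex (men 134–167, women 117–155 g/L). A value of 125 g/L is normal for a woman and low for a man, and Table 2 pools the sexes.
- P-alb limits depend on age band. A value of 35 g/L is normal only at 70 and over, and Table 2 pools ages.
- Means and SDs of change do not give a share normal at all.
- Table 2 describes the whole cohort, whereas each Table 3 column covers only patients uncensored at that week.

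**5. Why restricting to abnormal baselines is not a full answer.** Take a single cut-off with q = 50%, no treatment effect, and bivariate normal values with correlation ρ. The share normal both times is j = 1/4 + arcsin(ρ)/(2π), and the apparent normalisation among abnormal baselines is (0.5 − j)/0.5. For ρ = 0.5, j = 0.333 and the result is 33%; for ρ = 0.9, j = 0.428 and the result is 14%. Regression to the mean alone produces this. The model fits only P-CRP among the seven, since the other ranges are two-sided.

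**The case against.** The strongest reply is that the SAP carries out the objectives as the protocol words them. The protocol writes a baseline restriction into h and none into t–z, and a share normal among all patients is a valid descriptive quantity. That stands: the calculation is not wrong. The mismatch lies in the name and in the missing comparator. It affects seven row headings and the SAP 5.1 entries.

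A second reply is that baseline quartiles and change summaries are planned for every marker, and that protocol section 8.7 foresees longitudinal models of change against baseline. This stands in part. For P-CRP the quartiles do bracket the baseline share, so it would be too strong to say that the planned outputs tell a reader nothing. For the other six markers they are weak or cannot give the share, and SAP 7.2 does not carry the longitudinal models forward.

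A reader might also infer that the response and sub-score endpoints (c, e, f, r, s) share the defect, because a patient with a very low baseline score cannot meet those criteria. The documents do not support treating that as an error. Response over all patients is a legitimate descriptive denominator, and how many patients would be affected is unknown.

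**Conclusion.** The point holds for t–z: the label does not match the calculation, and no planned output gives the share normal at baseline. The effect on any row lies between nothing (if nobody is normal at baseline) and the whole reported percentage (if nobody normalises). Where it falls cannot be determined, since q, k and r are all assumed above.

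A reader might conclude that the rows will overstate effectiveness by a known or large amount; the documents give no baseline distribution to support that. Nor is the primary characterisation objective compromised. The affected outputs are secondary and descriptive, and the study has no hypotheses. Severity is minor to moderate, and the correction is worth making before tables are produced because it is nearly free.

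**What to change.** 1. In SAP 7.2 (t–z), SAP 5.1 (including the separate B-hb line) and the seven Table 3 headings, call the quantity the proportion with a normal level. A short note under t–z in SAP 2.2, like those already placed under b, c, e and q, would explain the difference from the protocol wording. Protocol section 8.7 lets the SAP modify the protocol's plans and ties an amendment to major changes of primary endpoints.
2. For each marker and timepoint, add the number and percentage normal at baseline among the same patients, using the sex- and age-specific limits, and the number without a baseline value.
3. Optionally, add the proportion normal among patients outside the range at baseline, with the number at risk and a note on regression to the mean. Keep it supplementary.

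No new data are needed, since baseline values are already collected. The cost is a few more table cells, some possibly masked: protocol section 8.6 bars export of groups under five patients. Every added cell, and any group that can be derived by subtraction from a neighbouring row, needs checking against that limit.

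The optional row also loses precision. With q from 0.2 to 0.8 the number at risk is 80 to 20 for N = 100 and 120 to 30 for N = 150, before censoring and missing values. At r = 30% the 95% half-width, 1.96·√(0.3·0.7/n), runs from 8 points (n = 120) to 20 points (n = 20). At q = 0.9 only 10–15 are at risk. If 30% normalise, that is 3–4.5 patients, under the limit; if 50% do, it is 5–7.5. Whether a row is withheld therefore has to be decided marker by marker.

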8 TABLE SHELLS

Table 2: Table shell for patient characteristics for primary objective

				n	missing
Variable	categories	mean (sd)	Median (25Q-75Q)	(%)	%
age				-	
sex	male	-	-		
	female	-	-		
weight				-	
height				-	
(BMI)				-	
smoking	current	-	-		
	ex-smoker	-	-		
	non-smoker	-	-		
age at UC diagnosis				-	
duration of UC				-	
Montreal classification	E1	-	-		
	E2	-	-		
	E3	-	-		
Mayo-score				-	
F-calpro				-	
P-CRP				-	
B-thromb				-	
P-alb				-	
B-leuk				-	
B-ly				-	
B-neutr				-	
B-hb				-	
Endoscopic findings	yes	-	-		
	no	-	-		

Table 3: Table shell for outcome objectives

Objective	Outcome	Week 8	Week 16	week 24	week 52
1	N patients	N	N	N	N
P1 - a	Proportion of patients on treatment	n (%)	n (%)	n (%)	n (%)
P1 - b	Proportion of patients with clinical remission (full Mayo)	n (%)	n (%)	n (%)	n (%)
P1 - b	Proportion of patients with clinical remission (partial Mayo)	n (%)	n (%)	n (%)	n (%)
P1 - c	Proportion of patients with clinical response (partial Mayo)	n (%)	n (%)	n (%)	n (%)
P1 - c	Proportion of patients with clinical response (full Mayo)	n (%)	n (%)	n (%)	n (%)
P1 - d	Proportion of patients with steroid free clinical remission	n (%)	n (%)	n (%)	n (%)
P1 - g	Proportion of patients with f-calpro reduction ≥50%	n (%)	n (%)	n (%)	n (%)
P1 - g	Proportion of patients with f-calpro reduction ≥75%	n (%)	n (%)	n (%)	n (%)
P1 - g	Proportion of patients with f-calpro reduction ≥90%	n (%)	n (%)	n (%)	n (%)
P1 - h	Proportion of patients reaching f-calpro below 250 mg/kg, of those that had f-calprotectin above 250 mg/kg at baseline	n (%)	n (%)	n (%)	n (%)
P1 - h	Change in f-calpro, among patients with f-calprotectin above 250 mg/kg at baseline	Δ -from baseline (mean ± sd)	Δ-from baseline (mean ± sd)	Δ-from baseline (mean ± sd)	Δ-from baseline (mean ± sd)

Objective	Outcome	Week 8	Week 16	week 24	week 52
P1 - i	Proportion of patients in sustained remission (pMayo) from week 8	-	n (%)	n (%)	n (%)
P1 - i	Proportion of patients in sustained remission (full Mayo score) from week 8	-	n (%)	n (%)	n (%)
P1 - j	Proportion of patients in sustained remission (pMayo) from week 16	-	-	n (%)	n (%)
P1 - j	Proportion of patients in sustained remission (full Mayo score) from week 16	-	-	n (%)	n (%)
P1 - k	Proportion of patients in sustained steroid free remission (pMayo) from week 16	-	-	n (%)	n (%)
P1 - k	Proportion of patients in sustained steroid free remission (full Mayo score) from week 16	-	-	n (%)	n (%)
P1 - l	Change in partial Mayo score	Δ-from baseline (mean ± sd)	Δ-from baseline (mean ± sd)	Δ-from baseline (mean ± sd)	Δ-from baseline (mean ± sd)
P1 - l	Change in full Mayo score	Δ-from baseline (mean ± sd)	Δ -from baseline (mean ± sd)	Δ-from baseline (mean ± sd)	Δ-from baseline (mean ± sd)
	Proportion of patients in sustained endoscopic remission (sub score = 0), mucosal healing (sub score 0-1) or endoscopic response (sub score				
P1 - m	reduction from baseline of ≥1) from week 8	-	n (%)	n (%)	n (%)

Objective	Outcome	Week 8	Week 16	week 24	week 52
P1 - n	Proportion of patients in physician assessed histological remission determined as inactive disease, or normal histology, and change from baseline in histology assessment (0= normal histology, 1= inactive disease and 2 = active disease)	n (%)	n (%)	n (%)	n (%)
P1 - o	Proportion of patients in sustained steroid free remission (pMayo and full Mayo score) (for all patients and for those treated with corticosteroids at baseline) and endoscopic remission (sub score = 0), mucosal healing (sub score 0-1) or endoscopic response (sub score reduction from baseline of ≥1) from week 8	-	n (%)	n (%)	n (%)
P1 - q	Proportion of patients with corticosteroid tapering	n (%)	n (%)	n (%)	n (%)
P1 - q	Corticosteroid tapering rates	mean ± sd	mean ± sd	mean ± sd	mean ± sd
P1 - q	Corticosteroid tapering doses	mean ± sd	mean ± sd	mean ± sd	mean ± sd
P1 - r	Proportion of patients with improvement in stool frequency sub score of 1 or more points and change from baseline in stool frequency sub score	n (%)	n (%)	n (%)	n (%)

Objective	Outcome	Week 8	Week 16	week 24	week 52
	Proportion of patients with improvement in				
P1 - s	rectal bleeding sub score of 1 or more points	n (%)	n (%)	n (%)	n (%)
		Δ-from baseline	Δ-from baseline	Δ-from baseline	Δ-from baseline
P1 - s	change from baseline in rectal bleeding sub score		(mean ± sd)	(mean ± sd)	(mean ± sd)
	Proportion of patients reaching normal P-CRP				
P1 - t	levels (below 4mg/L)	n (%)	n (%)	n (%)	n (%)
P1 - t	change from baseline in P-CRP levels	Δ-from baseline (mean ± sd)	Δ -from baseline (mean \pm sd)	Δ -from baseline (mean \pm sd)	Δ-from baseline (mean ± sd)
Ρ1-ι	Change Ironi baseline in F-CKF levels	(mean ± su)	(mean ± su)	(mean ± su)	(IIIeaii±Su)
	Proportion of patients reaching normal B-hb				
P1 - u	levels (men: 134–167 g/L, women: 117–155 g/L)	n (%)	n (%)	n (%)	n (%)
		Δ-from baseline	Δ-from baseline	Δ-from baseline	Δ-from baseline
P1 - u	change from baseline in B-hb levels	(mean ± sd)	(mean ± sd)	(mean ± sd)	(mean ± sd)
	Proportion of patients reaching normal B-leuk				
P1 - v	levels (3.4-8.2 x 10 ⁹ /L)	n (%)	n (%)	n (%)	n (%)
		Δ-from baseline	Δ-from baseline	Δ-from baseline	Δ-from baseline
P1 - v	change from baseline in B-leuk levels	(mean ± sd)	(mean ± sd)	(mean ± sd)	(mean ± sd)
	Proportion of patients reaching normal B-Thromb				
P1 - w	(150–360 x 109/L)	n (%)	n (%)	n (%)	n (%)
		Δ-from baseline	Δ-from baseline	Δ-from baseline	Δ-from baseline
P1 - w	change from baseline in B-Thromb levels	(mean ± sd)	(mean ± sd)	(mean ± sd)	(mean ± sd)

Objective	Outcome	Week 8	Week 16	week 24	week 52
P1 - x	Proportion of patients reaching normal B-ly (1.3-3.6 x 109/L)	n (%)	n (%)	n (%)	n (%)
P1 - x	change from baseline in B-ly levels	Δ-from baseline (mean ± sd)	Δ-from baseline (mean ± sd)	Δ -from baseline (mean ± sd)	Δ-from baseline (mean ± sd)
P1 - y	Proportion of patients reaching normal B-neutr (1.5-6.7 x 109/L)	n (%)	n (%)	n (%)	n (%)
P1 - y	change from baseline in B-neutr levels	Δ -from baseline (mean ± sd)	Δ -from baseline (mean ± sd)	Δ-from baseline (mean ± sd)	Δ-from baseline (mean ± sd)
P1 - z	Proportion of patients reaching normal P-alb (18-39 years: 36-48 g/L, 40-69 years: 36-45 g/L, 70 years and over: 34-45 g/L)	n (%)	n (%)	n (%)	n (%)
P1 - z	change from baseline in P-alb levels	Δ -from baseline (mean ± sd)			
P1 - bb	Proportion of patients with higher dose (10mg) of tofacitinib	n (%)	n (%)	n (%)	n (%)

Table 4: table shell to repost previous treatments

	Value
	mean ±
Number of treatments	sd
corticosteroids	n (%)
5-ASA	n (%)
Azathioprine	n (%)
6-Merkatopurin	n (%)
Methotrexate	n (%)
Cyclosporine	n (%)
Ustekinumab	n (%)
Vedolizumab	n (%)
Adalimumab	n (%)
Infliximab	n (%)
Golimumab	n (%)
